5.7.1. Other Anti-tumor/Anti-cancer or Experimental Drugs

Additional anticancer treatment including chemotherapy, hormonal therapy, radiotherapy (with the exception of palliative radiation as described in [Section 5.7.8](#)), or experimental anticancer medications are not permitted while patients are receiving study treatment. Additionally, the concurrent use of herbal supplements for an anti-cancer treatment is not permitted.

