5.7.7. Surgery

Caution is advised on theoretical grounds for any surgical procedures during the study. The appropriate interval of time between surgery and PF-06801591 required to minimize the risk of impaired wound healing and bleeding has not been determined. Stopping PF-06801591 is recommended at least 7 days prior to surgery. Postoperatively, the decision to reinitiate PF-06801591 treatment should be based on a clinical assessment of satisfactory wound healing and recovery from surgery.

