5.7.8. Radiation Therapy

Palliative radiotherapy to a limited field is allowed after consultation with Pfizer's medical monitor at any time during study participation, including during screening, unless clearly indicative of disease progression.

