- Complete response: Complete disappearance of all target lesions with the exception of nodal disease. All target nodes must decrease to normal size (short axis <10 mm). All target lesions must be assessed.
- Partial response: Greater than or equal to 30% decrease under baseline of the sum of diameters of all target measurable lesions. The short diameter is used in the sum for target nodes, while the longest diameter is used in the sum for all other target lesions. All target lesions must be assessed.
- Stable: Does not qualify for CR, PR, or progression. All target lesions must be assessed. Stable can follow PR only in the rare case that the sum increases by less than 20% from the nadir, but enough that a previously documented 30% decrease no longer holds.
- Objective progression: 20% increase in the sum of diameters of target measurable lesions above the smallest sum observed (over baseline if no decrease in the sum is observed during therapy), with a minimum absolute increase of 5 mm.
- Indeterminate: Progression has not been documented, and:
 - one or more target measurable lesions have not been assessed.
 - or assessment methods used were inconsistent with those used at baseline.
 - or one or more target lesions cannot be measured accurately (eg, poorly visible unless due to being too small to measure).
 - or one or more target lesions were excised or irradiated and have not reappeared or increased.

Non-target disease

- CR: Disappearance of all non-target lesions and normalization of tumor marker levels. All lymph nodes must be 'normal' in size (<10 mm short axis).
- Non-CR/Non-PD: Persistence of any non-target lesions and/or tumor marker level above the normal limits.
- PD: Unequivocal progression of pre-existing lesions. Generally the overall tumor burden must increase sufficiently to merit discontinuation of therapy. In the presence of SD or PR in target disease, progression due to unequivocal increase in non-target disease should be rare.

- Indeterminate: Progression has not been determined and one or more non-target sites were not assessed or assessment methods were inconsistent with those used at baseline.

New Lesions

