- Overall immune-related partial response (irPR): Sum of the diameters (longest for non-nodal lesions, shortest for nodal lesions) of target and new measurable lesions decreases $\geq 30\%$.

- Overall immune related stable disease (irSD): Sum of the diameters (longest for non-nodal lesions, shortest for nodal lesions) of target and new measurable lesions is neither irCR, irPR, (compared to baseline) nor immune related progressive disease (irPD, compared to nadir).
- Overall irPD: Sum of the diameters (longest for non-nodal lesions, shortest for nodal lesions) of target and new measurable lesions increases $\geq 20\%$ (compared to nadir) with a minimum absolute increase of 5 mm, confirmed by a repeat, consecutive observation at least 4 weeks from the date first documented.

New measurable lesions: Incorporated into tumor burden (ie, added to the target lesion measurements). A lymph node has to be ≥ 15 mm in short axis to be a measurable new lesion and its short axis measurement is included in the sum. Up to 2 new lesions per organ and up to 5 new lesions in total can be added to the measurements at each assessment time point.

New non measurable lesions: Do not define progression but preclude irCR.

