- Lesions that meet the criteria for radiographically defined simple cysts should not be considered as malignant lesions (neither measurable nor non-measurable) since they are, by definition, simple cysts.
- ‘Cystic lesions’ thought to represent cystic metastases can be considered as measurable lesions, if they meet the definition of measurability described above. However, if non-cystic lesions are present in the same patient, these are preferred for selection as target lesions.

Lesions with prior local treatment:

- Tumor lesions situated in a previously irradiated area, or in an area subjected to other loco-regional therapy, are usually not considered measurable unless there has been demonstrated progression in the lesion.

Solitary lesions:

If a measurable disease is restricted to a solitary lesion, its neoplastic nature should be confirmed by cytology/histology.

Recording Tumor Measurements

All measurable lesions up to a maximum of 2 lesions per organ and up to 5 in total and representative of all involved organs should be identified as target lesions and measured and recorded at baseline and at the stipulated intervals during treatment. Target lesions should be selected on the basis of their size (lesions with the longest diameters) and their suitability for accurate repetitive measurements (either by imaging techniques or clinically).

The longest diameter will be recorded for each target lesion. The sum of the longest diameter of all target lesions will be calculated and recorded as the baseline sum diameter to be used as reference to further characterize the objective tumor response of the measurable dimension of the disease during treatment.

One exception to the above described approach is related to pathological lymph nodes. Pathological lymph nodes are defined as measurable lesions and may be identified as target lesions if the criterion of a short axis of ≥ 15 mm by CT scan is met. Only the short axis of these nodes will contribute to the baseline sum. Nodal size is normally reported as two dimensions in the plane in which the image is obtained (for CT scan this is almost always the axial plane; for MRI the plane of acquisition may be axial, sagittal or coronal). The smaller of these measures is the short axis.

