A sum of the diameters (longest for non-nodal lesions, short axis for nodal lesions) for all target lesions will be calculated and reported as the baseline sum diameters. The baseline sum diameters will be used as reference to further characterize any objective tumor regression in the measurable dimension of the disease.

All other lesions (or sites of disease) should be identified as non-target lesions and should also be recorded at baseline. Measurements are not required and these lesions should be followed as 'present', 'absent', or in rare cases 'unequivocal progression'. In addition, it is possible to record multiple non-target lesions involving the same organ as a single item on the case record form (eg, 'multiple enlarged pelvic lymph nodes' or 'multiple liver metastases').

Definition of Tumor Response

Target Lesions

Response in target lesions is defined as follows:

Complete Response (CR): disappearance of all target lesions.

- **Partial Response (PR):** at least a 30% decrease in the sum of diameters of target lesions, taking as reference the baseline sum diameters.

- **Progressive Disease (PD):** at least a 20% increase in the sum of diameters of target lesions, taking as reference the smallest sum on study (this includes the baseline sum if that is the smallest on study). In addition to the relative increase of 20%, the sum must also demonstrate an absolute increase of at least 5 mm. The appearance of one or more new lesions is also considered a sign of progression.
- **Stable Disease (SD):** neither sufficient shrinkage to qualify for PR nor sufficient increase to qualify for PD, taking as reference the smallest sum diameters while on study.

When nodal disease is included in the sum of target lesions and the nodes decrease to ‘normal’ size (<10 mm), they may still have a measurement reported on scans. This measurement should be recorded even though the nodes are normal in order not to overstate progression should it be based on increase in size of the nodes. As noted earlier, this means that patients with CR may not have a total sum of ‘zero’ on the CRF.

Non-Target Lesions

While some non-target lesions may actually be measurable, they need not be measured and instead should be assessed only qualitatively at the time points specified in the protocol.

Response in non-target lesions is defined as follows:

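### irRECIST, one of the two criteria for the Part 2 primary ORR, has no rule for irradiated or excised target lesions, so shrinkage from local treatment can count as irPR

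*Protocol*

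**What the plan says.** **Local treatment during the study**
- Protocol 5.7.8: "Palliative radiotherapy to a limited field is allowed after consultation with" the sponsor's medical monitor, "at any time during study participation, including during screening, unless clearly indicative of disease progression".
- Protocol 5.7.1 bars other anticancer treatment on study but carves this out: "radiotherapy (with the exception of palliative radiation as described in" 5.7.8).
- Protocol 5.7.7 does not prohibit surgery: "Caution is advised on theoretical grounds for any surgical procedures during the study". It foresees restarting drug after the operation. Tumour resection is neither named nor excluded.

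**Response criteria**
- Protocol Appendix 3 (RECIST 1.1) lists, among the grounds for an Indeterminate target response, "or one or more target lesions were excised or irradiated and have not reappeared or increased". Table 7 carries an indeterminate target response through to an Indeterminate overall status, unless non-target disease or a new lesion shows progression.
- Protocol Appendix 4 (irRECIST) defines irPR as "Sum of the diameters (longest for non-nodal lesions, shortest for nodal lesions) of target and new measurable lesions decreases" by 30% or more. Table 9 in Appendix 5 has rows for irCR, irPR, irSD and irPD only. SAP 9.5 repeats the Appendix 4 definitions.
- SAP 9.4 restates RECIST 1.1 with PR as "at least a 30% decrease in the sum of diameters of target lesions, taking as reference the baseline sum diameters". Its only text on local treatment concerns which lesions are measurable at baseline: "Tumor lesions situated in a previously irradiated area, or in an area subjected to other loco-regional therapy, are usually not considered measurable".

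**Endpoint**
- Protocol 2.2 and SAP 3.1 and 6.2.3 make ORR by both RECIST 1.1 and irRECIST primary in Part 2. SAP 6 plans unconfirmed and confirmed versions of each.

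**The concern.** The sponsor recognised in Appendix 3 that a lesion which shrinks after radiotherapy or excision says nothing about the drug, and made such visits unusable for response. The same patient at the same visit, scored under irRECIST as written, can be a responder. That puts shrinkage from local treatment into one of the two forms of a primary endpoint.

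The contrast between irORR and ORR is also affected. It is meant to show delayed or flare-type responses, but part of it could come from a different treatment of irradiated lesions. Responses counted this way would also enter irDOR and time to response under irRECIST.

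Two features leave irRECIST more exposed than RECIST 1.1:
- Patients may stay on treatment after an initial radiological progression, so there is more time for local treatment to precede a counted irPR.
- Table 9 still gives irPR when the sum falls by 30% or more while non-index disease unequivocally progresses. A treated target lesion could therefore yield irPR alongside progression elsewhere.

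**Working it through.** **Step 1. The texts side by side, for a visit after a target lesion was irradiated and shrank**

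| Text | Rule for a treated target lesion | Indeterminate outcome available | Result if the sum is down by 30% or more |
|---|---|---|---|
| Protocol Appendix 3 and Table 7 | Yes | Yes | Indeterminate |
| Protocol Appendix 4 and Table 9 | None | No | irPR |
| SAP 9.5 | None | No | irPR |
| SAP 9.4 | None after baseline | NE if not all target lesions evaluated, but a treated lesion is not said to be one of these | PR on the SAP text taken alone |

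**Step 2. How much one lesion must shrink.** If the treated lesion makes up share w of the baseline sum and shrinks by fraction s, with the others unchanged, the sum falls by w × s. irPR needs w × s ≥ 0.30, so s ≥ 0.30/w.
- w = 1 (single target lesion): s ≥ 0.30
- w = 0.5: s ≥ 0.60
- w = 0.33: s ≥ 0.91
- w = 0.2: s ≥ 1.5, so this lesion alone cannot do it

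Entry requires only one measurable lesion (Part 2 inclusion criterion 7), so large shares are possible.

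**Step 3. The plan's own precision figure.** Protocol 9.3 states, for an ORR of 19% with N = 70, an 80% CI of 13.4 to 25.2% and a 90% CI of 12.2 to 27.3%. The Wilson score interval is [p + z²/2n ± z√(p(1−p)/n + z²/4n²)] / (1 + z²/n). At 13/70 = 18.6% it gives 13.36 to 25.22% and 12.15 to 27.33%, so the stated figures reproduce. They are not in dispute.

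**Step 4. Effect per misclassified responder.** One patient adds 1/n: 1/70 = 1.4 points for NSCLC and 1/30 = 3.3 points for urothelial carcinoma. The SAP still carries 60 and 40, which would give 1/60 = 1.7 and 1/40 = 2.5 points.

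The documents give no rate, so the number of extra responders below is an assumption. Intervals are exact 95% CIs, the method in SAP 5.3.2.

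| Extra responders | NSCLC irORR, base 13/70 |
|---|---|
| 0 | 18.6% (10.3 to 29.7) |
| 1 | 20.0% (11.4 to 31.3) |
| 2 | 21.4% (12.5 to 32.9) |
| 3 | 22.9% (13.7 to 34.4) |

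For urothelial carcinoma, with an illustrative base of 6/30 = 20.0%, one extra gives 23.3% and two give 26.7%.

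**Step 5. The 30-patient look.** With the prior beta(0.235, 1) and x responders of 30, the posterior is beta(0.235 + x, 31 − x). P(ORR > 10%) is 0.69 at x = 4 (the plan says about 70%), 0.85 at x = 5 and 0.94 at x = 6. The look uses unconfirmed responses and is presented separately by criterion. The plan does not say which criterion feeds the posterior, so this applies only if irRECIST does.

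**Step 6. Does confirmation protect?** No. A second scan at least 4 weeks later does not separate drug effect from local treatment, because shrinkage after local treatment can persist.

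**The case against.** **The rule carries over from RECIST 1.1.** This is the strongest reply. Appendix 4 presents irRECIST as built on RECIST 1.1 and names two contrasts, confirmation and new lesions; treated lesions are not among them. It also omits other RECIST 1.1 conventions, such as merging lesions and missing assessments, so it is not exhaustive. The reading is arguable, but no text states it. Appendix 4 gives its own full definitions, and neither it nor Table 9 offers an outcome in which the rule could be recorded. Sites could reasonably differ.

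**RECIST 1.1 is protected.** This largely stands. A reader might infer from SAP 9.4 that RECIST ORR is inflated too. The documents do not support that: by-visit ORR in SAP 6.2.3 uses investigator responses, and Protocol 7.4 sends investigators to Appendix 3, which keeps the rule.

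**Surgery.** A reader might infer that 5.7.7 authorises resection of target lesions. It is a caution about wound healing and bleeding, and 5.7.1 excepts only palliative radiation. Radiotherapy is the firm route; excision is a possibility left open.

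**Screening.** A reader might infer that a lesion irradiated after the baseline scan must remain a target lesion at its earlier size. Appendix 3 and SAP 9.4 make previously irradiated lesions generally non-measurable, so that does not follow. What is unsettled is the order of scan and radiotherapy within the 28-day window.

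**Few patients.** Probably so. Radiotherapy must be palliative, limited-field, discussed with the medical monitor and not clearly a sign of progression. Bone disease without a qualifying soft-tissue component is not measurable in any case. A reader might infer an inflation of several points, but the documents give no frequency to support one.

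**Phase 1 estimation only.** There is no hypothesis test, and the two criteria are reported separately, so ORR under Appendix 3 remains visible. That limits the damage but does not make irORR right.

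**Conclusion.** The point holds for irRECIST. On-study palliative radiotherapy is expressly allowed, and the irPR definition as written credits any fall of 30% or more in the sum to response, while the protocol's own RECIST 1.1 text would call the same visit Indeterminate. irORR, a Part 2 primary endpoint, can be biased upward, and its difference from RECIST ORR can partly reflect local treatment.

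For RECIST 1.1 the finding is narrower. SAP 9.4 omits a protocol rule, and this matters only if best overall response is derived or checked from SAP 9.4 instead of from investigator assessments under Appendix 3. SAP 6.2.3 refers to a derivation of best overall response without naming its source.

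The size is 1.4 points per misclassified NSCLC responder and 3.3 per urothelial responder, on planned enrolment of 70 and 30. The number of such patients cannot be derived from the documents. The conclusion assumes that irRECIST is applied as written, without an unstated carry-over of the Appendix 3 rule.

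**What to change.** Carry the Appendix 3 rule for excised or irradiated lesions into Protocol Appendix 4 and Table 9, and into SAP 9.4 and 9.5:
- After local treatment of a target lesion, or of a new lesion counted in the irRECIST sum, later visits are indeterminate/NE for response unless progression is shown.
- A response documented before the local treatment still counts in the unconfirmed analysis.
- The same rule applies to a target lesion irradiated between the baseline scan and C1D1, in line with the measurability text in Appendix 3 and SAP 9.4.

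The change is to response scoring only and leaves patient management as it is.

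The costs are a slightly lower irORR, a few more NE visits, and some genuine responses from before local treatment that can no longer be confirmed, which pulls confirmed irORR down. There is also a data requirement. Protocol 5.7 records non-drug interventions by name, route, duration and reason; anatomical site is not listed. The sponsor should make sure that the treated site is captured so that it can be matched to the target-lesion list.

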Appendix 5. Overall Response Derived from Changes in Index, Non-index, and New Lesions

Overall responses derived from changes in index, non-index, and new lesions are outlined in Table 9.

Table 9. Overall Response Derived from Changes in Index, Non-index, and New Lesions

Measurable response	Non-measurable response		Overall response using irRECIST ^b
	Non-Index Lesions	Measurable Lesions	
Index and New Measurable Lesions (Tumor Burden)^a			
Decrease 100%	Absent	Absent	irCR
Decrease 100%	Stable	Any	irPR
Decrease 100%	Unequivocal progression	Any	irPR
Decrease ≥30%	Absent/stable	Any	irPR
Decrease ≥30%	Unequivocal progression	Any	irPR
Decrease <30% and increase <20%	Absent/stable	Any	irSD
Decrease <30% and increase <20%	Unequivocal progression	Any	irSD
Increase ≥20%	Any	Any	irPD

a. Decrease assessed relative to baseline.

b. Response (irCR and irPR) and progression (irPD) must be confirmed by a second, consecutive assessment at least 4 weeks apart.

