Appendix 4. Immune-related RECIST (irRECIST)

Increasing clinical experience indicates that traditional response criteria may not be sufficient to fully characterize activity in this new era of targeted therapies and/or biologics.

This is particularly true for immunotherapeutic agents such as anti-cytotoxic T lymphocyte-associated protein-4 (CTLA-4) and anti PD-1/anti-PD-L1 antibodies which exert the antitumor activity by augmenting activation and proliferation of T cells, thus leading to tumor infiltration by T cells and tumor regression rather than direct cytotoxic effects.^{1,58,59} Clinical observations of patients with advanced melanoma treated with ipilimumab, for example, suggested that conventional response assessment criteria such as Response Evaluation Criteria in Solid Tumors (RECIST) and WHO criteria are not sufficient to fully characterize patterns of tumor response to immunotherapy because tumors treated with immunotherapeutic agents may show additional response patterns that are not described in these conventional criteria.

Furthermore, the conventional tumor assessment criteria (RECIST and WHO criteria) have been reported as not capturing the existence of a subset of patients who have an OS similar to those who have experienced CR or PR but were flagged as PD by WHO criteria.^{60,61,62}

On these grounds, a tumor assessment system has been developed that incorporates these delayed or flare type responses into the RECIST v1.1 (irRECIST).

For irRECIST, only target and measurable lesions are taken into account. In contrast to RECIST v1.1, irRECIST:

- Requires confirmation of both progression and response by imaging at least 4 weeks from the date first documented; and
- Does not necessarily score the appearance of new lesions as PD if the sum of lesion diameters of target lesions (minimum of 10 mm longest diameter per non-nodal lesion and 15 mm shortest diameter per nodal lesion, maximum of 5 target lesions, maximum of 2 per organ) and measurable new lesions does not increase by $\geq 20\%$.

The same method of assessment and the same technique should be used to characterize each identified and reported target lesion(s) at baseline and throughout the trial.

irRECIST is defined as follows:

- Overall immune related complete response (irCR): Complete disappearance of all lesions (whether measurable or not) and no new lesions. All measurable lymph nodes also must have a reduction in short axis to < 10 mm.

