6.2.3. ORR (Part 2)

ORR, as assessed using RECIST version 1.1 and irRECIST, is a primary efficacy endpoint for Part 2. The following analyses will be performed in the mITT population by tumor type (NSCLC or urothelial carcinoma) and pooled:

1. ORR by visit, separately for RECIST 1.1 and irRECIST: investigator provided tumor response CR, PR, and CR+PR will be presented by descriptive statistics (frequency and percentage) and 95% confidence interval.
2. Best overall response of CR, PR, and CR+PR, separately for RECIST 1.1 and irRECIST. This will include best overall response derivation without confirmation and with confirmation. Descriptive statistics (frequency and percentage) and 95% confidence interval will be provided.

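### Table 9 (Appendix 5) does not match the irRECIST definitions in Appendix 4 and SAP 9.5, and no document says whether irPR or irPD applies when a sum meets both

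*Protocol*

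**What the plan says.** Table 9 assigns irPR to a fall in tumor burden of 30% or more and irPD to a rise of 20% or more. Its only statement of a reference point is footnote a: "Decrease assessed relative to baseline". The irPD row has no reference point and no minimum size of increase. The irCR row needs a 100% decrease. Footnote b adds that "Response (irCR and irPR) and progression (irPD) must be confirmed by a second, consecutive assessment at least 4 weeks apart".

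Appendix 4, repeated in SAP 9.5, is more specific. The rise that defines irPD is "compared to nadir) with a minimum absolute increase of 5 mm, confirmed by a repeat, consecutive observation" at least 4 weeks later. irSD is what "is neither irCR, irPR, (compared to baseline) nor immune related progressive disease (irPD, compared to nadir") covers, so response is judged from baseline and progression from nadir. For irCR, "All measurable lymph nodes also must have a reduction in short axis to" below 10 mm. Target nodes start at a minimum of "15 mm shortest diameter per nodal lesion".

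ORR by RECIST 1.1 and by irRECIST is a Part 2 primary endpoint (Protocol 2.2). SAP 6.2.3 reports CR, PR and CR+PR. For the by-visit analysis, "investigator provided tumor response CR, PR, and CR+PR will be presented by descriptive statistics". SAP Section 6 analyses the irRECIST versions of ORR, PFS, DOR and TTP both with and without confirmation.

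**The concern.** A reader who applies Table 9 as printed can reach a different category from one who applies Appendix 4 to the same measurements. This happens in three ways: the reference for the increase, the missing 5 mm floor, and residual nodes at irCR. A further gap is common to Table 9, Appendix 4 and SAP 9.5. A patient with a deep response followed by regrowth can be far enough below baseline for irPR and far enough above nadir for irPD, and nothing says which prevails.

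At stake are the split of responders between irCR and irPR, the date of progression used in irPFS, irDOR and irTTP, and in a narrow case the confirmed irORR. Protocol 3.1 also ties continuation of treatment to irRECIST progression and to confirmed irCR, so the same inconsistency reaches conduct as well as analysis.

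**Working it through.** The plan states no figure on this point, so the check is to apply the rules to example sums. Write B for the baseline sum, N for the nadir and C for the current sum, in mm. The thresholds are those of Table 9 and Appendix 4.

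**1. Reference point and 5 mm minimum**

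| Sums over time | Table 9, increase read from baseline | Table 9, increase read from nadir | Appendix 4 / SAP 9.5 |
|---|---|---|---|
| 100, 40, 60 | irPR (40% below B) | irPR row and irPD row (50% above N) | irPR and the irPD threshold (+50%, +20 mm) |
| 100, 80, 100 | irSD (no change from B) | irPD (25% above N) | irPD threshold (+25%, +20 mm) |
| 20, 24 | irPD (+20%) | irPD (+20%) | irSD (rise of 4 mm, below 5 mm) |

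Neither reading of the Table 9 irPD row reproduces Appendix 4 throughout. Read from baseline, the first patient reaches irPD only at 1.2 × 100 = 120 mm, three times the nadir of 40.

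**2. When irPR and irPD are both met (increase from nadir)**

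- irPR: C ≤ 0.70 × B.
- irPD threshold: C ≥ 1.20 × N and C − N ≥ 5 mm.
- Both need 1.20 × N ≤ 0.70 × B, so N ≤ (0.70 / 1.20) × B = 0.583 × B. The best decrease is then at least 41.7%. There must also be room for the 5 mm rise, that is N + 5 ≤ 0.70 × B.
- Examples (B, N, C): 100, 40, 60; 100, 50, 65; 50, 20, 30.

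Read from baseline, C cannot be both ≤ 0.70 × B and ≥ 1.20 × B. The overlap then disappears, but only by departing from the nadir rule.

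**3. Nodes at irCR**

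- A target node going from at least 15 mm to below 10 mm falls by more than (15 − 10) / 15 = 33.3%. With every other lesion at 0 mm the sum therefore always falls by more than 30%.
- Example: non-nodal 40 to 0 mm and node 20 to 8 mm. The decrease is (60 − 8) / 60 = 86.7%. With no non-target disease and no new lesions this is irCR under Appendix 4 and irPR under Table 9.
- The patient is a responder either way, so CR+PR does not move.

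**4. Effect on the endpoints**

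- *Unconfirmed irORR (best response).* The overlap requires an earlier scan at least 41.7% below baseline. That scan already counts as irPR, so nothing changes. Only the by-visit entry for the rebound scan differs.
- *Confirmed irORR.* With 100, 40, 60 the first irPR is at 40 and the confirmatory scan is the 60. If that scan is irPR, the response is confirmed; if irPD prevails, it is not. With 100, 40, 38, 60 the response is confirmed before the regrowth and nothing changes. One such patient is worth 1/70 = 1.4 points in NSCLC or 1/30 = 3.3 points in urothelial cancer (planned sizes, Protocol 9.3).
- *irPFS, irDOR, irTTP.* If the 60 mm scan is called irPR, progression is dated at a later scan or not at all.
- *irCR and irPR counts.* Each patient with residual normalised nodes moves from one count to the other.

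**The case against.** The strongest reply is that Appendix 4 governs. Protocol 7.4 points to Appendices 3 and 4 for response and does not cite Appendix 5, and SAP 9.5 reproduces Appendix 4 without Table 9. A careful assessor would take the nadir reference and the 5 mm floor from Appendix 4. This stands as a limit on practical reach. It does not remove the mismatch, because Table 9 is the only table in either document that combines lesion changes into an irRECIST category, and the by-visit responses come from investigators.

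It is also fair to say that 100, 40, 60 is not yet irPD under Appendix 4, since irPD needs a confirming scan. But the SAP also runs analyses without confirmation, and even with confirmation the category at the 60 mm scan has to be settled first.

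Several stronger readings are tempting and do not hold:

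- A reader might infer that the irPR/irPD overlap is a contradiction between the appendices. It is not: the same overlap and the same silence on precedence sit inside Appendix 4 and SAP 9.5.
- A reader might infer that nodal disease can never reach irCR in Table 9. A node recorded as 0 mm does reach a 100% decrease. The problem is confined to nodes that normalise but remain measurable. The rule that such nodes keep their measurement is in the RECIST 1.1 text (Appendix 3; SAP 9.4) and is carried over to irRECIST by inference.
- It can be argued that Appendix 4 itself opens irCR with disappearance of all lesions. But its nodal clause would then be redundant, since a vanished node is already below 10 mm.
- A reader might infer that Table 9 lacks a row for a 100% decrease with a new non-measurable lesion. A 100% decrease is also a decrease of at least 30%, and that row already gives irPR.

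**Conclusion.** The point holds, with limited reach. Table 9 omits the nadir reference and the 5 mm minimum for irPD, and has no allowance for nodes below 10 mm at irCR. Separately, Table 9, Appendix 4 and SAP 9.5 all leave precedence between irPR and irPD unstated for sums whose nadir is at or below 58.3% of baseline. Where Table 9 is followed, irCR versus irPR counts and the progression dates behind irPFS, irDOR and irTTP can be wrong.

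A reader might infer that the primary irORR is generally unreliable. The documents do not support that: the nodal point cannot change irORR, unconfirmed irORR is unaffected, and confirmed irORR moves only when the confirmatory scan is the rebound scan.

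The 1.4 and 3.3 points are per reclassified patient at the planned sizes of 70 and 30. The documents give no basis for how often this would occur, and the mITT denominators may be smaller. The conclusion assumes that some investigator responses are assigned from Table 9, and that residual node sizes stay in the irRECIST sum.

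**What to change.** For the response derivation:

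1. In Table 9, label the irPD row as an increase of at least 20% and at least 5 mm from nadir, with a reference to Appendix 4.
2. In Table 9, Appendix 4 and SAP 9.5, state that meeting the irPD threshold takes precedence over irPR and irSD at that assessment, subject to the confirmation rule.
3. In the irCR row of Table 9, replace the 100% decrease by the Appendix 4 condition: all lesions absent and nodes below 10 mm in short axis.

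No extra row is needed. Because irPD and confirmed irCR also bear on continuing treatment (Protocol 3.1), the protocol passages must be reconciled with each other; this point takes no position on the treatment rule itself.

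The cost is two row edits and one sentence in three places. No new data are needed, because lesion measurements already recorded allow categories to be re-derived.
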